#### 6.6.1.3.3 *Causality*

The Investigator will assess the causality/relationship between the study drug and the AE and record that assessment in the e-CRF. Causality will be assessed as:

- **Not related:** AE is obviously explained by another cause; OR the time of occurrence of AE is not reasonably related to administration of the study drug
- **Possibly related:** Study drug administration and AE occurrence are reasonably related in time; AND AE is explained equally well by causes other than study drug
- **Probably related:** Study drug administration and the occurrence of the AE are reasonably related in time; AND the AE is more likely explained by exposure to study drug than by other mechanisms

The most likely cause of an AE (e.g., disease under treatment, concomitant disease, concomitant medication, other) will be indicated in the e-CRF with details of the concomitant disease or medication or other cause.

#### 6.6.1.3.4 *Adverse events related to laboratory assessments*

Abnormal laboratory findings (e.g., biochemistry, haematology, urinalysis) or other abnormal assessments (e.g., vital signs) that are judged by the Investigator as clinically significant will, if certain requirements are met, be recorded as AEs or SAEs. Clinically significant abnormal laboratory findings or other abnormal assessments that meet the definition of an AE or SAE and are detected during the study, or are present at baseline and significantly worsen following the start of the study, will be reported as AEs or SAEs.

The Investigator will exercise their medical and scientific judgment in deciding whether an abnormal laboratory finding or other abnormal assessment is clinically significant and as such an AE.

#### 6.6.1.4 *Recording Adverse Events*

AE reporting will extend from signing of informed consent. AEs occurring after D28 should be reported to the Sponsor by the Investigator if the Investigator considers there is a causal relationship with the study drug. However, all deaths will be recorded and reported as SAEs throughout the study (up until D90).

All AE reports should contain a brief description of the event, date and time of onset, date and time of resolution, intensity, treatment required, relationship to study drug, action taken with the study drug, outcome, and whether the event is classified as serious.

Recording a diagnosis (when possible) is preferred to recording a list of associated signs and symptoms. However, if a diagnosis is known but there are associated signs or symptoms not generally attributed to the diagnosis, the diagnosis and each sign or symptom must be recorded separately.

### 6.6.1.5 Reporting Serious Adverse Events

According to applicable US and European Union regulations and requirements, an SAE must be reported to the Sponsor from the trial site as soon as possible **within 24 hours** of becoming aware of the SAE. A medically qualified person at the trial site identified on the Delegation of Authority Log with this responsibility must assess the SAE. Any member of the clinical trial site staff can assist in reporting an initial SAE. The Principal Investigator or delegated sub-investigators are responsible for the SAE reporting procedures at the site during the trial, and must always sign-off on each SAE even if other site staff have reported the event on behalf of the investigators. A delegation log at each trial site will clearly show delegation of responsibilities regarding SAE reporting.

The SAE reporting is done via the eCRF system. Paper forms are available as back-ups.

The Investigator and the Sponsor (or Sponsor's designated agent) will review each SAE report and the seriousness and the causal relationship of the event to study treatment will be evaluated. In addition, the Sponsor (or Sponsor's designated agent) will evaluate the expectedness according to the reference document (Investigator Brochure). Based on the Investigator and Sponsor's assessment of the event, a decision will be made concerning the need for further action.

If consensus on the assessment cannot be reached between the parties (e.g., Investigator and Sponsor/Sponsor's delegate), all opinions will be provided in the Council for International Organizations of Medical Sciences Form I report and reporting to the CA and IEC/IRB should be based on the highest degree of causality provided.

Details for reporting SUSARs can be found in [Section 6.6.1.7](#).

All SAEs will be recorded that occur between signing of informed consent and D28. Events occurring after D28 and coming to the attention of the Investigator should be reported only if they are considered in the opinion of the Investigator to be causally related to the investigational drug. However, all deaths up to D90 will be reported as SAEs.

All SAEs occurring as described above, must be reported **within 24 hours**.

The minimum information required for an initial report is:

- Details of person sending the report (i.e., name and address of Investigator)
- Patient identification details (screening/randomization number, age, sex, NOT patient name)
- Protocol number
- Description of SAE
- Causality assessment

However, all points on the SAE report should be covered in the initial report.

After receipt of the initial report, Pharmacovigilance (PV) will review the information and, if necessary, contact the Investigator to obtain further information for assessment of the event. PV CRO will be responsible for all information processing and reporting according to local legal requirements.

Detailed instructions concerning SAE reporting procedures will be described in a Safety Management Plan written by PV CRO. SAE Report Form and contact information for reporting SAEs will be provided to the sites.

#### **6.6.1.6 Follow-up of Adverse Events**

All AEs experienced by a patient, irrespective of the suspected causality, will be monitored until: the AE has resolved or any abnormal laboratory values have returned to baseline, or stabilised at a level acceptable to the Investigator and Medical Monitor; there is a satisfactory explanation for the changes observed; the follow-up period is completed (D90) or the patient is lost to follow-up; or the patient has died.

#### **6.6.1.7 Suspected Unexpected Serious Adverse Reactions**

Any AE that is serious, associated with the use of the study drug, and unexpected (SUSAR) has additional reporting requirements, as described below.

- If the SUSAR is fatal or life threatening, associated with use of the study drug and unexpected, regulatory authorities and IECs/IRBs must be notified **within 7 calendar days** after the Sponsor learns of the event. Additional follow-up information (cause of death, autopsy report and hospital report) should be reported **within an additional 8 days** (15 days total).
- If the SUSAR is not fatal or life threatening but is otherwise serious, associated with the use of the study drug and unexpected, regulatory authorities and IECs/IRBs must be notified **within 15 calendar days** after the Sponsor learns of the event.

The Sponsor will notify the Investigators in a timely fashion of relevant information about SUSARs that could adversely affect the safety of patients. Follow-up information may be submitted if necessary.

The Sponsor will also provide annual safety updates to the regulatory authorities and IECs/IRBs responsible for the study. These updates will include information on SUSARs and other relevant safety findings.

### **6.7 Pregnancy**

Pregnancy is an exclusion criterion, and a pregnancy test is performed in all women of childbearing potential at screening. Owing to the nature of the study involving short (6-day) treatment with the study drug in a hospital setting, it is not practically possible for women to become pregnant during treatment and for there to be any foetal exposure to the study drug. Study subjects and their partners are advised not to become pregnant for 2 months after the study drug exposure and to use appropriate contraception. Any pregnancy during the study (for 2 months after the study drug exposure) that becomes to the knowledge of an investigator during the study, should be reported as an SAE and followed-up for the outcome. Any pregnancy, which onset is after 2 months from the study drug exposure, until the end of the study, will be reported (as a non-SAE) and followed-up for the outcome.

## **7 STATISTICAL METHODS**

The statistical considerations summarised in this section outline the plan for data analysis of this study.

The main analysis and reporting will use D14 and D28 data after last study subject has completed D28 assessment and the data has been verified and locked. D90 follow-up data is analysed separately.

Before unblinding/database lock, a separate Statistical Analysis Plan (SAP) will be finalised, providing detailed methods for the analyses outlined below. Before the conduct of interim analysis, an Interim Analysis (IA) plan will be finalised. After the clinical parts of the study have been completed, a blinded review of the data will be undertaken according to the SAP/IA plan. This review will make decisions regarding: the handling of missing data and data for withdrawn patients; and the definition of the Per-Protocol Set (PPS) at the patient level.

Any deviations from the planned analyses will be described and justified in the final integrated study report.

## 7.1 Study Patients

### 7.1.1 Disposition of Patients

Disposition and reasons for discontinuation will be summarised for all patients together with study drug exposure and study duration by treatment group.

The number and percentage of patients entering and completing each phase of the study will be presented by treatment group. Reasons for withdrawal pre- and post-randomization will also be summarised.

The disposition of patients will also include information on the number and percentage of patients who:

- completed study drug and follow-up
- withdrew from study drug but completed follow-up
- withdrew from study drug and from follow-up

### 7.1.2 Protocol Deviations

Deviations from the protocol including violations of inclusion/exclusion criteria will be classified as “minor” or “major” in conjunction with the Sponsor and Medical Monitor. Relevant major deviations from the protocol will lead to the exclusion of that patient from the PPS. Deviations will be defined prior to unblinding.

### 7.1.3 Analysis Sets

The following analysis sets will be defined for statistical analysis:

The **Full analysis set (FAS)** will consist of all randomized patients who have been received at least one dose of study drug. If a randomized subject becomes ineligible before dosing the subject will be replaced and is excluded from the FAS. The primary efficacy analyses will be based on this data set. Patients will be included in the analysis according to the treatment to which they were randomized.

The **Per-Protocol Set (PPS)** will consist of patients in the FAS excluding patients with major protocol violations. A list of major protocol violations relevant for excluding data from the PPS will be detailed in the SAP before the interim analysis. The precise definition of the PPS at the patient level will be identified at the blinded data review meeting before the interim and final analyses.

Statistical analyses for the primary and secondary endpoints will be performed on both the FAS and PPS.

The **safety set** will consist of all patients who receive at least one dose of study drug. All safety and tolerability analyses will be based on this analysis set. A patient who receives the wrong treatment according to their randomisation will be analysed for safety and tolerability in the treatment group corresponding to the treatment received.

Statistical analyses for the primary and secondary endpoints will be performed on both the FAS and PPS. The primary efficacy endpoint analysis will be based on the FAS; a secondary analysis will also be performed based on the PPS to assess the sensitivity of the analysis to the choice of analysis set. All safety analyses will be based on the safety set. Demographic and baseline characteristics will be evaluated for the FAS.

## 7.2 General Considerations

All statistical tests will be two sided and will be performed at the significance level of 0.05, unless otherwise stated.

Continuous data will be summarised by treatment group using descriptive statistics (number, mean, median, standard deviation [SD], minimum and maximum). Categorical data will be summarised by treatment group using frequency tables (frequencies and percentages).

### 7.2.1 Analysis and Data Conventions

#### 7.2.1.1 Definition of Baseline

The baseline assessment, where relevant, will be the latest available valid pre-dose assessment.

#### 7.2.1.2 Visit Windows

Assessments made outside of protocol-mandated windows will be displayed according to the e-CRF assessment recorded by the Investigator.

#### 7.2.1.3 Unscheduled Assessments

Extra assessments (laboratory data or vital signs associated with non-protocol clinical visits or obtained in the course of investigating or managing AEs) will be included in listings, but not summaries. If more than one laboratory value is available for a given visit, the first valid observation will be used in summaries and all observations will be presented in listings. It is noted that invalid laboratory data will not be used (from haemolysed samples, mishandled samples, quantity not sufficient, or other conditions that would render values invalid).

#### 7.2.1.4 Missing Data Handling

In general, data will not be imputed for the primary efficacy analysis or the safety analysis. For other efficacy analyses, where relevant, imputations will use the last observation carried forward method for patients in the analysis. Additional details will be given in the SAP.

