# 6 STUDY CONDUCT AND ASSESSMENTS

## 6.1 General Considerations

The study will utilize standard clinical care laboratory assessments for safety, in order to avoid excessive sampling of blood in hospitalized subjects. Complete Blood Count (CBC), White Blood Cells (WBC) differential and biochemistry, for example, will be collected from clinical routine if available; if not then these will be collected as protocol specific assessments from pre-dose D1, D2-D7, D10, D14, D28/last day in hospital. The timing of the assessments is shown in the [Table 2](#) Schedule of Procedures (below). Laboratory assessments needed for CBC, differential and chemistry should be taken on the timepoints indicated in the [Table 2](#), if not available by clinical standard of care (i.e., analyses should not be duplicated if available by clinical routine).

For the purposes of this study, study day 1 (D1) is defined as the first calendar day (from midnight to the following midnight) of treatment with IFN beta-1a or dexamethasone. All days thereafter are defined as "Dn" (e.g., D2, D3, etc.) until D28.

Baseline assessments are defined as those assessments carried out in the screening period and pre-dose D1 (before the first dose of study drug on D1). Unless withdrawn from study or discharged from the hospital, all patients will receive study drug for 6 consecutive days (D1-D6). All assessments in the period up to D28 are only to be performed when a patient is in hospital. Study assessment at D14, D28 and D90 are performed by phone call if the patient is not any longer present at the hospital, or sought through records if the patient cannot be contacted. The end of the study will be the date of last patient/last visit at D90.

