**Table 2. Schedule of procedures and assessments**

Procedure	Screening	D1 pre-dose	D1-D6	D7-D14 	D15-D27	D28 short-term follow-up 	D90 long-term follow-up (+/- 7 days)
Informed consent	X						
Inclusion/exclusion criteria	X	X					
Demographics	X						
Medical history	X						
Physical examination (incl. weight and height at screening)	X					X	
Pregnancy test in women of childbearing potential	X						
Review and documentation of available lung X-ray / CT scan	X						
Genetic sample		X 					
Randomization		X					
Administration of study drug			X				
Specimen collection  :							
MxA		X	X	X			
CD73		X	X	X			
PIMs 		X	X	X			
IFN beta		X	X	X			
ADAs		X				X	
COVID-19 test (if positive result of a test taken within the last 7 days is not available)	X						
COVID-19 for viral load PCR 		X	X	X			
Nasopharyngeal swab for virus variant analysis		X					
Biochemistry, CBC & Differential 		X	X	X		X	
Data collection from medical records:	X	X	X	X		X	X
WHO 9-point ordinal scale		X	X 	X 		X 	
Previous and concomitant medications and interventional therapies	X	X	X 	X 	X 	X 	
Clinical status assessments 		X	X	X	X	X	X
Vital signs 		X	X	X	X	X	
Adverse events 	X	X	X 	X 	X 	X 	X

*All daily assessments should be obtained at the same time as D1 pre-dose assessment (+/- 2 hours). The specimen collections and assessments at pre-dose D1 should be within 4 hours prior to the administration of study drug.*

1. *If the subject is not in the hospital, information to be collected by phone on D14 and D28*
2. *Short term follow-up; D28 or Day of discharge from hospital (whichever is earlier).*
3. *Blood collection for MxA, CD73 and PIMs will occur: pre-dose on D1, D3, D5; and on D7 for hospitalized patients (for IFN blood collection will occur: pre-dose D1, D1(5 minutes after D1 dosing), pre-dose on D3 and on D7). Blood collection for ADA will occur: pre-dose D1 and D28 or Day of discharge from hospital (whichever is earlier).*
4. *PIM = Potential Inflammatory and interferon signalling Markers on a protein and RNA level (Nanostring); DNA for genetic analyses will be extracted from the pre-dose PIM sample*

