## 6.4 Post-Discharge Assessments

Patients will be contacted at D14, D28 (if discharged; assessment window of +/- 3 days permitted, but with exact assessments for D14 and D28 conditions) and D90 (if discharged; assessment window of +/- 1 week permitted) to assess for health status, including mortality. At D14 and D28 the patient will be assessed on changes in the concomitant medications and on possible adverse events. On D90 only survival and hospital status will be collected. At the time of enrolment, subjects will be asked to provide at least two methods of contact, as well as contact information for a caregiver, to facilitate contact at Day 90. Patients who cannot be reached by phone will be mailed a follow up letter. The information is sought through records if the patient cannot be contacted.

Please see section 6.3. for patients that have been discharged from the hospital but are re-admitted due to COVID-19 before D28 to the study site.

## 6.5 Withdrawal Prior to Day 28

For patients withdrawing from the study, procedures for the last day of study involvement should be followed.

In the case of an ongoing AE, appropriate safety evaluations and/or additional tests may be performed at any time when clinically indicated at the discretion of the attending physician or Investigator, until resolution or Day 28, whichever is first. Any ongoing AEs should be followed up to resolution or Day 28, whichever is the sooner.

If the patient refuses to have any of the above assessments, or if the patient is lost to follow-up, then this should be noted in the e-CRF. If a patient is lost to follow-up, wherever possible, mortality data will be sought from alternative sources, such as the patient's local physician or available national databases and all data obtained reported as SAEs.

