### **7.5.2 Secondary Efficacy Analyses**

For the Secondary Efficacy Endpoint WHO OSCI score at Day 28 will be analysed in a similar ordinal logistic regression model than the primary endpoint.

The primary analysis of the mortality endpoints (in-hospital and overall (all-cause) mortality at Days 28 and 90) will be based on the FAS and will be undertaken using COX proportional hazards regression model adjusting for age, gender and ethnicity key baseline characteristics. This analysis will be repeated using the PPS as a sensitivity analysis. Hazard ratios comparing the treatment groups will be reported using 95% CI for these endpoints. Data for these efficacy endpoints will also be presented for key predefined subgroups of patients (such as SNP rs9984273, see [Section 4.2.3](#)) together with 95% CIs for the difference in those rates to supplement the investigation of homogeneity.

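### Last observation carried forward for the Day 28 ordinal score can leave a patient with a documented discharge scored as hospitalised; a small defect with a cheap fix

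*Protocol*

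**What the plan says.** Protocol 7.2.1.4 has two rules. For the primary endpoint: "In general, data will not be imputed for the primary efficacy analysis or the safety analysis". For the rest: "For other efficacy analyses, where relevant, imputations will use the last observation carried forward method for patients in the analysis". Further detail is deferred to the SAP.

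The second rule covers the Day 28 score, because under 7.5.2 "WHO OSCI score at Day 28 will be analysed in a similar ordinal logistic regression model than the primary endpoint".

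How the score is collected:

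- Table 2 marks the ordinal scale at pre-dose Day 1, Days 1-6, Days 7-14 and Day 28, with no mark under Days 15-27.
- Section 6.1 says: "All assessments in the period up to D28 are only to be performed when a patient is in hospital". For discharged patients, Table 2 footnote 1 says: "If the subject is not in the hospital, information to be collected by phone on D14 and D28".
- If the call fails, 6.1 has the assessment "or sought through records if the patient cannot be contacted", and 6.4 repeats this: "The information is sought through records if the patient cannot be contacted". Section 6.4 allows a window of 3 days either side, "but with exact assessments for D14 and D28 conditions". Section 4.8.1.1 requires at least two calls and one letter.
- Table 2 footnote 2 places the short-term follow-up on Day 28 or the day of discharge, whichever comes first.

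Hospital status (Table 2, including Days 15-27), discharge disposition and readmission to the study site (6.3) are recorded separately from the ordinal score.

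**The concern.** Scores 3 to 7 all mean that the patient is in hospital, and a discharged patient belongs at 2 or below. Carrying the last score forward ignores the discharge itself. A patient whose record shows that he or she went home can therefore enter the Day 28 model in the middle of the scale instead of at its good end, and no section says that a known discharge overrides the carried value.

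What is at stake is the estimate for one secondary endpoint. If non-contact is equal in the two arms, the arms are pulled together. If it is unequal, the arm with more missed contacts looks worse than it was.

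**Working it through.** **1. Which patients the rule can misplace.** All cases assume a Day 28 score still missing after calls, letter and records search.

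- *Discharged before Day 14, scored at home on Day 14.* The carried value is an out-of-hospital score, so this error does not arise.
- *Discharged before Day 14, no Day 14 score either.* The last score is from the ward, and 3 or more is carried.
- *Discharged on Days 15-27.* The last score is the Day 14 in-hospital score or, through footnote 2, a discharge-day score. The documents do not say whether the discharge day is scored as hospitalised or not. If hospitalised, 3 or more is carried.

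The score can stay missing while discharge is known, because a hospital record may show that the patient went home without showing activity limitation, which separates 1 from 2.

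**2. The plan's own figure.** Section 7.4 gives 80% power for the Day 14 score with odds ratio 0.43 and 70 evaluable patients per arm; section 7.2 sets two-sided 0.05. The Whitehead formula is

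power = Φ( √[ n · ln(OR)² · (1 − Σp³) / 6 ] − 1.960 ),

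where p are the category proportions averaged over the arms. These are not in the documents. With five equally filled categories, Σp³ = 5 × 0.2³ = 0.04, ln(0.43)² = 0.7123, and √(70 × 0.7123 × 0.96 / 6) = 2.824, so power = Φ(0.864) = 80.6%. Four to nine equal categories give 79.7-81.7%. The stated figure reproduces. I take 0.43 as the odds of a worse score on interferon relative to dexamethasone; power is the same if the ratio is inverted.

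**3. Share of home patients affected (all inputs assumed).** Let f be the proportion with the Day 28 score missing after every attempt, L the proportion discharged on Days 15-27, and m the proportion of the remainder who also lack a Day 14 score:

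share = f × [L + (1 − L) × m].

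Example: 0.05 × (0.10 + 0.90 × 0.30) = 1.85%. With L of 5-20% and m of 20-50%, the share is 0.5-1.2% at f = 2%, 1.2-3.0% at f = 5% and 2.4-6.0% at f = 10%. This counts every late discharge as carrying an in-hospital score, so it is an upper figure for given f, L and m. I take 1-2.5% as the working range.

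**4. Effect on the Day 28 comparison.** Assumed control distributions over scores 0-8:

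- 60% home: .10, .25, .25, .06, .12, .07, .05, .03, .07
- 75% home: .15, .35, .25, .03, .06, .04, .03, .02, .07
- 85% home: .20, .40, .25, .03, .04, .02, .01, .01, .04

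The interferon arm is the proportional-odds shift with odds ratio 0.43. The given share of scores 0-2 is moved to 3 and/or 4 in both arms, the proportional-odds model is fitted to the resulting population, and power follows from the formula in step 2 with 70 per arm.

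| Control home | Power, complete | 1% moved: OR; power | 2.5% moved: OR; power |
|---|---|---|---|
| 60% | 0.804 | 0.433-0.434; 0.796-0.798 | 0.438-0.440; 0.783-0.789 |
| 75% | 0.792 | 0.435-0.436; 0.780-0.782 | 0.442-0.444; 0.763-0.766 |
| 85% | 0.782 | 0.437; 0.767-0.768 | 0.446-0.448; 0.745-0.748 |

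The loss is 0.6-1.5 points at 1% and 1.6-3.7 points at 2.5%. In patients, this runs from 70 × 0.60 × 0.01 = 0.4 to 70 × 0.929 × 0.025 = 1.6 per arm (92.9% being the interferon share home when control is 85%). A rank-sum simulation of the same settings (12,000 runs) gave 0.80, 0.79 and 0.78 with complete data and 0.78, 0.75 and 0.73 at 2.5%: the same order of loss, slightly larger in the last setting.

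**5. Unequal non-contact.** With no true effect and 5% of home patients moved in one arm only, the fitted odds ratio lies between 0.88 and 1.14, depending on which arm is affected. A 5% gap is beyond the working range; it is shown only to establish that the direction is not fixed.

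**The case against.** The strongest reply is that the plan leaves a detail open rather than ordering an error. LOCF applies only where relevant, more detail was to come in the SAP, and section 7 reserves missing-data decisions for a blinded review. Records are searched for every non-contact, and hospital status is among the items sought (6.3.3), so few scores should remain missing. The loss in the working range is small against a standard error of about 0.30 for the log odds ratio (0.844 / 2.802, from the stated 80% power), on an endpoint with no power claim.

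Most of this stands, and it sets the priority. It does not remove the point: the only rule written down is the one that can contradict the record, and none of these provisions states a better one.

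Stronger readings that the documents do not support:

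- *No score can exist after Day 14 for a late discharge.* Footnote 2 can place a scored visit on the discharge day, and both the synopsis and 6.3 provide for assessments while in hospital. The open question is how that day is coded.
- *Every discharged patient who misses the Day 28 call is miscoded.* A patient scored at home on Day 14 is not, and records may supply the Day 28 score.
- *The primary result is exposed.* The LOCF rule excludes the primary analysis.
- *The rule creates false benefit.* With equal non-contact it only dilutes a true effect.
- *Reported results are affected.* The SAP tests no hypotheses and only lists and describes data from five patients.

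**Conclusion.** The concern holds as a limited defect in the protocol's analysis plan. Read as written, the rule can assign a hospitalised score at Day 28 to a patient whose discharge is documented. At 1-2.5% of home patients miscoded, this moves a true odds ratio of 0.43 to about 0.433-0.448 and costs about 0.6-3.7 power points. Those figures rest on assumed category distributions, equal miscoding in both arms, and Day 28 having the same effect size and numbers as the Day 14 calculation; the documents supply none of these for Day 28. The change is worth making because it is cheap and removes scores that the trial's own data would contradict, but it is optional and low priority.

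**What to change.** In 7.2.1.4, do not use LOCF as the main rule for the Day 28 ordinal score. Derive the score from known status at Day 28:

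- dead: 8;
- in hospital: the recorded level of support;
- documented discharge, with no readmission found in the study-site data or the records search: not hospitalised, at most 2.

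Where the exact home category (0, 1 or 2) is unknown, use multiple imputation restricted to 0-2, with a sensitivity analysis setting all such patients to 2. Keep LOCF at most as a further sensitivity analysis.

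The gain is modest. In the settings of step 4, setting every unknown to 2 recovers about 0.3-1.4 of the lost power points. The recovery under multiple imputation was not calculated.

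The cost is protocol or SAP wording and a little programming; no visits, tests or patients are added. One weakness remains: 6.3 describes readmission data only for the study site, so a patient readmitted elsewhere and not found in the records would be scored as home.
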